# 1 Introduction

## 1.1 Background

Atrial fibrillation (AF) is the most common disturbance of heart rhythm. With a UK prevalence of 7.2% in patients aged 65 and over and 10.3% in patients aged 75 and over [1] AF has considerable impact on quality of life and NHS resources[2][3]. Treatment of AF and its consequences (anti-arrhythmic & anti-coagulant drugs, hospital monitoring & stroke treatment) are expensive for the NHS and implementation of the recent NICE guidelines (June 2006)[2] on management of AF is estimated to cost £21.86m per year[3]. The NHS devotes 5% of its budget to strokes and 15% of these are associated with AF[1]. Routine anticoagulation is used to reduce the risk of stroke, however this incurs an increased risk of bleeding and the burden of monitoring treatment falls on general practice, anticoagulant clinics and haematology laboratories.

AF ablation devices are a new and costly technology being marketed to treat this condition. Their use is increasing in NHS practice despite the lack of good research evidence to support adoption. Although there are instances of their use as a stand-alone procedure, they are already in use within the NHS as an adjunct procedure for patients having cardiac surgery for other problems.

### 1.1.1 Existing research

The current basis for treatment and management of AF is dealt with in a UK NICE Guideline (2006)[2] European Guidelines[4] and a Cochrane review[5]. International recommendations on surgical and catheter ablation of AF were published in 2007 jointly by the Heart Rhythm Society, European Heart Rhythm Association and European Cardiac Arrhythmia Society in their Expert Consensus statement[6]. The maze procedure can be performed in two ways:

1. The traditional cut-and-sew technique, known as the Cox-maze with its many modifications, is reliable in restoring sinus rhythm in the majority of patients (references cited in Calkins et al.[6]). Despite being available since 1987, this procedure has signally failed to achieve widespread use. The main reason for this is that it is technically demanding and adds substantially to the operative burden of a heart operation. It is currently in very limited use by a few surgeons in a few centres and tends to be reserved for otherwise fit patients with severely symptomatic AF who are prepared to take the risk of a major intervention to relieve their symptoms.

2. The ablation device maze procedure uses an energy source (heat, cold, radiofrequency or microwave) to replicate the lesion set of the Cox-maze. As a rule, the

procedure is safe, well tolerated and only adds minimal increase in time and burden of the operation.

Common sense suggests that treating AF at the time of cardiac surgery is advantageous to the patient. However the only evidence supporting this comes from 5 small randomised controlled trials of ablation devices as adjuncts to surgery[7][8][9][10][11]. These trials found that SR was restored in 44-94% of treated patients compared to 5-33% of controls. The trials were small and follow-up was short. Success was mostly defined on the basis of a single ECG recording. No trial looked at patient-centred outcomes or cost effectiveness. Despite this lack of robust evidence, an increasing number of patients with AF having open heart surgery are now being offered concomitant ablation maze procedures (cited in Calkins et al.[6]).

The 2007 Expert Consensus Statement on Catheter and Surgical Ablation of Atrial Fibrillation[6] developed by Heart Rhythm Society in partnership with European Heart Rhythm Association and European Cardiac Arrhythmia Society launched a call for high quality prospective multicentre trials to adopt consistent definitions of procedural success in long term assessments of the safety and efficacy of ablation.

The relevance of the Amaze trial is highlighted by the 2010 consensus statement from international cardiothoracic surgeons[12]. This statement emphasises the urgent need for adequately powered and properly designed and reported randomised trials to measure clinically relevant outcomes (e.g. stroke, symptom relief, QoL, long term mortality) and resource use[13]. In other words, dimensions of methodological quality and clinical relevance that are incorporated into the Amaze protocol.

### 1.1.2 Purpose of Amaze Trial

This trial responds to this call and will inform patients, clinicians and the NHS about the routine adoption of this technology. The study will test the hypothesis that treating AF by incorporating a modified maze procedure (using an ablation device) into elective cardiac surgery will promote a return to SR and improve quality of life as well as being cost-effective from an NHS perspective.

## 1.2 Study design

The Amaze trial is a pragmatic, multicentre, prospective, double blind, randomised controlled trial to compare clinical, patient-based and cost outcomes for patients with pre-existing AF who undergo routine cardiac surgery either with or without an adjunct device-based ablation procedure.

The trial is double blind to the extent that neither the patient nor the cardiologist who analyses the 4 day ECG, nor the quality of life assessor should be aware which group the patient has been allocated to.

Eligible patients are randomised (in a 1:1 ratio) to receive either their routine cardiac surgery with no additional procedure or their routine cardiac surgery with an additional device-based AF ablation procedure.

### 1.3 Study aims and objectives

#### 1.3.1 Intermediate Primary objective

To compare two groups for the rate of return to stable SR at 12 months as well as quality-adjusted survival over 2 years, 4-day ECG monitors will be used to assess the predominant rhythm (SR or AF) and the AF load, i.e. the percentage of time that the patient is in AF if the predominant rhythm is SR.

#### 1.3.2 Final Primary Objective

To compare Quality-Adjusted Survival in terms of Quality-Adjusted Life Years over two years between the two groups.

#### 1.3.3 Secondary Objectives

1. To determine whether the adjunct maze procedure improves the rate of return to stable SR at 24 months after surgery.

2. To determine whether the adjunct maze procedure decreases thromboembolic neurological complications (eg. stroke).

3. To determine whether the adjunct maze procedure enables anticoagulant treatment to be withdrawn safely.

4. To determine whether the adjunct maze procedure enables safe reduction or withdrawal of antiarrhythmic medication.

5. To determine whether the adjunct maze procedure is cost effective compared to the routine procedure.

## 1.4 Sample size and recruitment

### 1.4.1 Sample size calculation

Sample size calculations are based on both primary endpoints.

#### Return to SR at 12 months

Published RCTs of ablation as an addition to cardiac surgery have reported rates of return to SR at 12 months [7][8][9][10][11] ranging from 44% to 87% in the trial arms and 5% to 33% in the control arms. If we take a conservative estimate of the difference between the groups (45% vs. 30%) then we would have 80% power to detect this difference with a sample size of 176 in each group, total 352 (2-sided significance 5%). With recruitment of 400 patients this would allow for deaths or loss to follow up at 12 months of approximately 15%.

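### For return to SR at 12 months, 400 recruits against a requirement of 352 allow for 12% deaths or loss, not the approximately 15% stated

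*SAP*

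**What the plan says.** SAP section 1.4.1, under Return to SR at 12 months, assumes SR rates of 45% with the maze procedure and 30% without it, 80% power and a two-sided 5% level. It finds that power "with a sample size of 176 in each group, total 352". The next sentence turns this into a recruitment margin: "With recruitment of 400 patients this would allow for deaths or loss to follow up at 12 months of approximately 15" per cent. Section 1.2 gives the allocation as 1:1.

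No other section gives a different loss allowance or recruitment total for this endpoint. The same total of 400 appears under the quality-adjusted survival endpoint in section 1.4.1, as 200 per group.

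**The concern.** The margin sentence follows directly on the 352, so the allowance should be the share of 400 that can be lost while 352 remain. The three figures, 352, 400 and 15%, do not fit together: if 15% of 400 are lost, fewer than 352 are left.

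What is at stake is the accuracy of a stated design property of a primary endpoint. A reader who takes the sentence at face value would think that a loss of between 12% and 15% leaves the plan's required number in place, when it does not.

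**Working it through.** **Inputs**, all from SAP section 1.4.1 (Return to SR at 12 months), with the 1:1 allocation from section 1.2:

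- p1 = 0.45, p2 = 0.30, difference d = 0.15, mean rate 0.375
- two-sided 5% (z = 1.960), power 80% (z = 0.842)
- required: 176 per group, 352 in total
- recruited: 400, or 200 per group
- stated loss allowance: approximately 15%

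**Step 1. Reproduce the 352.** The usual two-proportion formula with pooled variance under the null is

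n = [1.960 × √(2 × 0.375 × 0.625) + 0.842 × √(0.45 × 0.55 + 0.30 × 0.70)]² / 0.15²

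This gives 162.3, so 163 per group. The continuity correction is

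n' = (n/4) × [1 + √(1 + 4/(n × d))]²

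With n = 162.3 this gives 175.4, so 176 per group and 352 in total, which matches the plan exactly. Other common variants do not match: unpooled variance gives 160 per group and the arcsine method 162. The SAP does not name its formula, so the continuity correction is an inference from this match.

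**Step 2. The loss that 400 can absorb.**

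- 400 - 352 = 48 patients
- 48/400 = 12.0%

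**Step 3. What a 15% loss leaves.**

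- 0.15 × 400 = 60 lost
- 400 - 60 = 340 left, or 170 per group
- 352 - 340 = 12 short of the requirement

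**Step 4. Could another convention give 15%?**

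- Loss as a share of the required number: 48/352 = 13.6%
- Inflating the requirement by 15%: 352 × 1.15 = 404.8, so 405, which is above 400
- Keeping 352 after a true 15% loss: 352/0.85 = 414.1, so 415

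None of these links 352 and 400 through 15%. The second comes closest and may be where the figure came from, but that is a guess.

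**Step 5. The size of the effect on power.** With the correction, power is Φ{[d - 1/n - 1.960 × √(2 × 0.375 × 0.625/n)] / √(0.4575/n)}, where 0.4575 = 0.45 × 0.55 + 0.30 × 0.70. Without it, the 1/n term is dropped.

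| Evaluable per group | Total | Loss from 400 | Power, corrected | Power, uncorrected |
|---|---|---|---|---|
| 176 | 352 | 12.0% | 80.1% | 83.1% |
| 170 | 340 | 15.0% | 78.6% | 81.8% |
| 163 | 326 | 18.5% | 76.8% | 80.2% |

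On the basis that reproduces the plan's number, moving from 12% to 15% loss costs 80.1 - 78.6 = 1.5 percentage points.

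**The case against.** The strongest reply is that the practical message, that 400 recruits cope with roughly 15% loss, is nearly true. The primary analysis in section 5.4 is a logistic regression with surgeon, procedure and baseline rhythm, and it specifies no continuity-corrected test. Without the correction 326 patients suffice, 400 recruits absorb 74/400 = 18.5% loss, and power at 15% loss is 81.8%. This stands as a statement about power. It does not rescue the sentence, because the plan sets its requirement at 352 and cannot also treat 340 as meeting it.

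Three further replies are weaker:

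- The word approximately does not cover the gap. 12% does not round to 15%, and the implied margin is 60 patients rather than 48.
- Section 2.3 imputes the missing rhythm of patients who withdraw or are lost, so they are not simply dropped. That is true, but imputation does not restore the full information, and it does not change the subtraction of 352 from 400.
- The 400 also serves the quality-adjusted survival endpoint. That is a good reason to leave recruitment alone, but not a reason for the SR allowance to be wrong in its own terms.

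A reader might infer that the trial uses this margin to judge whether follow-up loss has left the endpoint underpowered. The SAP does not support that. The 15% appears once and triggers nothing. The only attrition threshold is 5% withdrawn or lost before 12 months, which starts the sensitivity analyses (sections 2.3 and 5.4.1).

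**Conclusion.** The stated allowance is wrong as written: 352 and 400 give 12.0%, and a 15% loss leaves 340, which is 12 below the plan's own requirement. This part is plain arithmetic on figures in one paragraph and needs no assumption.

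The consequence is small. It amounts to about 1.5 points of power on the continuity-corrected basis, and power stays above 80% without the correction. The power figures assume the plan's 45% and 30%, equal groups after loss, an unadjusted two-group comparison and analysis of the remaining patients only. The corrected figures also assume the formula inferred in step 1.

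Two stronger readings are tempting and should not be drawn. The first is that the sample size is wrong; it is not, since 176 per group reproduces exactly. The second is that the trial must recruit 415. That number only shows what a true 15% allowance would require. The SAP gives no expected loss rate from which one could say that 12% is too thin, and the error changes no analysis, population or recruitment target.

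**What to change.** In SAP section 1.4.1 (Return to SR at 12 months), replace approximately 15% with 12%. No extra recruitment is needed.

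Optionally add that at 15% loss (170 per group) power would be about 78.6% with the continuity correction and about 81.8% without it. If this is added, the sponsor should first confirm which formula produced 176 per group, and name it.

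The cost is one sentence.

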#### Clinical effectiveness measured as quality-adjusted survival over 2 years

The emphasis in cost-effectiveness studies is on estimation rather than hypothesis testing so that formal sample size calculations are less important. However, we provide a power calculation based on the effectiveness measure QALY. We could find no studies reporting comparative QALYs in similar patients undergoing ablation and cardiac surgery. From previous studies of patients undergoing angiography for suspected ischaemic heart disease[14] and patients with refractory angina[15] the standard deviation of QALYs over 12 and 18 months is at most 0.3. Over follow up of 2 years the minimum clinically important improvement is considered to be one extra month of quality-adjusted life, or 0.083 QALYs. With a sample of 200 patients per group, total 400, we would have approximately 80% power to detect a difference of 0.083 QALYs, (2-sided significance 5%). If the accepted threshold for cost effectiveness were in the range £20-30,000 per QALY and we could demonstrate a significant increase in QALYs of 0.0833, then the procedure would be cost-effective for an incremental cost of at most £2,500.

## 1.5 Randomisation

Patients who fulfil the eligibility and have given written informed consent and have sufficient time for discussion and consideration, are randomised (in a 1:1 ratio) to one of two groups to receive either their routine cardiac surgery with no additional procedure or their routine cardiac surgery with an adjunct maze procedure.

Patient allocations are computer generated by the trial statistician and are in random permuted blocks of variable lengths, stratified by surgeon and by planned cardiac procedure (CABG, aortic valve, mitral valve, combined procedure).

## 1.6 Eligibility

Eligible patients are consecutive elective cardiac surgical patients undergoing major cardiac surgery (such as coronary, valve or combined operations) with a history of paroxysmal, persistent or chronic AF beginning more than 3 months before the date of the operation.

Paroxysmal AF is defined as recurrent AF (> 2 episodes) that terminates spontaneously within 4 days (Expert Consensus Statement on Catheter and Surgical Ablation of Atrial Fibrillation)[6].

Persistent AF is defined as AF which continues beyond 4 days.

Chronic or longstanding AF is persistent AF beyond 1 year.

### Inclusion criteria:

age over 18.

elective cardiac surgery planned (Coronary surgery, valve surgery, combined coronary and valve surgery, any other Cardiac surgery requiring cardiopulmonary bypass.)

history of documented atrial fibrillation (chronic, persistent or paroxysmal) beginning more than 3 months before entry into the study.

written informed consent to participation.

### Exclusion criteria:

previous cardiac operations.

emergency or salvage cardiac operations.

surgery without cardiopulmonary bypass.

unlikely to be available for follow-up over a two-year period.

deemed not competent to provide consent.

All randomised participants will be included in the final intention-to-treat analysis, except those for whom consent to use data was withdrawn, or written informed consent was not received. Deviations from these criteria will be summarised and reported.

## 2 Outcome

### 2.1 Primary outcomes

Rate of return to stable SR at 12 months- 4 day ECG monitors are being used to assess the predominant rhythm (SR or AF) and the AF load ie the percentage of time that the patient is in AF if their predominant rhythm is SR.

Clinical effectiveness quality adjusted survival over 2 years

### 2.2 Secondary outcomes

Clinical endpoints of SR at 24 months after surgery, overall survival and stroke-free survival, incidence of anticoagulant-related haemorrhage.

Health-related QoL measured by the EuroQoL, SF-36 and NYHA.

Resource use and cost-effectiveness of the adjunct maze procedure.

Anticoagulant and antiarrhythmic drug usage.

### 2.3 Missing data

Data management will focus on the consenting process, participant eligibility, safety, data consistency and test outcomes. Attempts will be made to retrieve missing data on these areas via a thorough data cleaning process.

The levels of missing data and reasons for missingness will be investigated for the consenting process, participant eligibility, safety, data consistency and test outcomes. The quantity of missing data will be monitored by treatment group, and a summary of the number of patients with missing primary endpoint data and the quantity of missing data by treatment group will be reported.

For the intermediate primary endpoint (return to sinus rhythm at 12 months), if a patient withdraws consent or is lost to follow-up for further participation within 12 months, multiple imputation used to impute missing outcome (AF or SR at 12 months) as a function of the baseline heart rhythm, surgeon, surgical procedure and treatment group. Rubin's rules will be used to combine imputed datasets. If more than 5% of patients are withdrawn or lost to follow-up before 12 months, then the outcome will be imputed under the alternative patterns as sensitivity analyses. (See section 5.4.1)

For the final primary endpoint (Quality-Adjusted Survival at 2 years), where a patient is deceased before the end of follow-up, the utility value of 0 will be imputed for all

subsequent assessments. If the response is missing, and the patient is not known to be deceased, the missing value will be imputed using the method of multiple imputation. A “Last Observation Carried Forward” approach will be used as an alternative imputation technique for imputing other (non-death) missing values in a sensitivity analysis.

The primary analysis model will only require the baseline rhythm, surgeon and surgical procedure which are immediately recorded when patients attend the preadmission clinic and has consented to participate or during the period of surgery, so there is little concerns about missing data arising in this model. If any missing values in the covariates are reported, they will be imputed using a function of the known covariates and primary outcomes of interest.

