### 4.3 Data collection during and after surgery

Data collection is based on the recommendations of Shemin et al.[13] and includes procedural details-including the lesion set in the experimental group. Data collected after surgery includes: mortality, stroke/thromboembolic events, medications, EuroQoL, health-related quality of life, cardioversion plan if appropriate, 4-day ECG recordings, resource use, adverse events.

Data are collected during surgery, at discharge, 6 weeks after surgery (at a routine service visit), at 6, 12 and 24 months after surgery during out-patient research visits and annually thereafter by telephone follow-up.

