## Return to SR

The intermediate primary outcome, whether patient returns to SR at 12 months, will be summarized according to the group to which they were randomised. The comparison between the heart rhythm (AF or SR) at the baseline and 12 months will be also summarized.

For the primary endpoint analysis, the rate in SR for Routine treatment group will be compared to that for Routine+Maze treatment group using a binary logistic regression model, which will include surgeon (as a random effect), surgical procedure and baseline heart rhythm as fixed effects. The odds ratio for the rate of return to SR at 12 months of Routine treatment group against Routine+Maze treatment group will be reported with 95% confidence interval and p-value for the data seen, under the null hypothesis that the rates of return to SR at 12 months are no different between the pairs of groups.

The adequacy of the logistic regression models for the primary endpoint will be assessed by examining the following statistics and relevant graphical summaries:

Pearson Residuals/Deviance (Half-normal plots)

Leverage values.

Cook's Distance.

Cross validation probabilities (the probability of a particular observation, conditional on the remaining observations).

L-statistics (the influence of an observation on the difference in deviance due to fitting an the treatment effect).

Actual percentage time in AF across the 4 days of monitoring at baseline and at 12 months, i.e. the percentage of time that the patient is in AF if their predominant rhythm is SR, is reported by treatment group. Based on the interim report, the percentage time

in AF is almost dichotomized at 0% and 100%. Therefore, only summary statistics are reported in this case.

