## 5.6 Key Secondary Endpoint Analysis

The key secondary endpoint, the rate to return stable SR at 24 months will be analysed in a similar way to the rate of return to SR at 12 month, but will include only those patients for whose measurements are available. The rate in SR at 24 months for Routine treatment group will be compared to that for Routine+Maze treatment group using a binary logistic regression model including baseline heart rhythm, surgeon, surgical procedure and treatment group. The odds ratio for the rate of return to SR at 24 months of Routine treatment group relative to the Routine+Maze group will be reported with 95% confidence interval and p-value for the data seen, under the null hypothesis that the rates of return to SR at 24 months are no different between the pairs of groups.

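### The imputation of missing 12-month rhythm uses only the analysis model's own variables, so it reproduces the complete-case result and ignores post-operative data that could reduce possible bias

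*SAP*

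**What the plan says.** SAP 2.3 covers patients who withdraw or are lost before 12 months. The rule is "multiple imputation used to impute missing outcome (AF or SR at 12 months) as a function of the baseline heart rhythm, surgeon, surgical procedure", plus treatment group, combined by Rubin's rules. SAP 5.4.1 extends imputation to any missing 12-month rhythm without naming predictors. If more than 5% are withdrawn or lost, it adds two sensitivity analyses: one sets lost patients to AF, the other leaves them out.

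The primary model in SAP 5.4 (Return to SR) compares the groups by logistic regression, "which will include surgeon (as a random effect), surgical procedure and baseline heart rhythm as fixed effects". The variables are therefore the same in both models.

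SAP 4.3 lists 4-day ECG recordings and any cardioversion plan among the post-surgery data. It then gives the visits: discharge, 6 weeks, and "at 6, 12 and 24 months after surgery during out-patient research visits". It does not say which visits include an ECG. Rhythm is explicit at baseline, 12 months and 24 months. EQ-5D (SAP 5.4) and drug use (SAP 5.8) are scheduled at discharge, 6 weeks and 6, 12 and 24 months.

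The 24-month rhythm analysis in SAP 5.6 "will include only those patients for whose measurements are available".

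**The concern.** Multiple imputation improves on complete cases when the imputation model holds something the analysis model lacks. Here it does not. A patient with a missing outcome whose covariates are all in the analysis model contributes nothing to the likelihood for the treatment effect, and imputing from those covariates cannot change that. The plan appears to deal with missing rhythm but in effect analyses complete cases.

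At stake is a primary endpoint. If staying in follow-up is related to the rhythm reached after surgery, and this relation differs by arm, the planned odds ratio carries the complete-case bias. The sensitivity analyses do not address this: leaving lost patients out treats them as the primary analysis in effect already does, and setting them to AF disregards anything recorded before loss.

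The same gap appears at 24 months. A patient with a known 12-month rhythm and no 24-month recording is dropped, although 12-month rhythm is certain to be scheduled and is likely to be informative.

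**Working it through.** **Inputs from the SAP.** Sinus rhythm 45% vs 30%, 80% power, 176 per group (1.4.1: "45% vs. 30%) then we would have 80% power to detect this difference with a sample size of 176 in each group, total 352"); two-sided 5%; 1:1 allocation; 400 recruited.

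**Reproducing the plan's figure.** The usual two-proportion formula gives
(1.960·√(2·0.375·0.625) + 0.842·√(0.45·0.55 + 0.30·0.70))² / 0.15² = 162.3, so 163 per group. With the continuity correction it is 176, as stated. Recruiting 400 for 352 evaluable allows 1 − 352/400 = 12% missing, which is the share used below. (The SAP says "With recruitment of 400 patients this would allow for deaths or loss to follow up at 12 months of approximately 15"%.)

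**Assumptions not in the SAP.** An earlier post-operative rhythm agrees with the 12-month rhythm in a share s of patients (0.80-0.95). Loss probabilities depend on that earlier rhythm: m₁ if SR, m₀ if AF.

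**Large-sample odds ratio in complete cases.** The chance of being observed is
- r₁ = s(1 − m₁) + (1 − s)(1 − m₀) for a patient in SR at 12 months,
- r₀ = s(1 − m₀) + (1 − s)(1 − m₁) for a patient in AF.

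Observed OR = true OR × (r₁/r₀ in the maze arm) / (r₁/r₀ in the control arm). The true OR, maze against routine, is (0.45/0.55)/(0.30/0.70) = 1.909. (The SAP reports the inverse ratio.)

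Worked case with s = 0.90, loss in the maze arm 6% if SR and 17% if AF, and 12% throughout in control:
- r₁ = 0.9·0.94 + 0.1·0.83 = 0.929
- r₀ = 0.9·0.83 + 0.1·0.94 = 0.841
- observed OR = 1.909 × 0.929/0.841 = 2.109

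| Loss pattern (SR / AF) | Observed OR, s = 0.80 to 0.95 | Bias in risk difference |
|---|---|---|
| Same in both arms (6% / 16%) | 1.909 | at most +0.3 points |
| Maze arm only (6% / 17%; control 12%) | 2.06 to 2.14 | +1.9 to +2.8 points |
| Opposite (maze 6% / 17%; control 20% / 8.5%) | 2.23 to 2.41 | +3.5 to +5.3 points |

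Equal dependence cancels from the odds ratio. The sign is not fixed. With control loss of 4% if SR and 18% if AF, flat loss in the maze arm and s = 0.85, r₁ = 0.939 and r₀ = 0.841 in control, so the observed OR is 1.909 × 0.841/0.939 = 1.71.

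**Does the planned imputation differ from complete cases?** Simulation: 600 trials per scenario, 200 per arm, about 12% missing, 20 imputations, Rubin's rules. Surgeon was left out for simplicity. Mean log odds ratios:

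| Scenario | Full data | Complete case | SAP imputation | Plus earlier rhythm |
|---|---|---|---|---|
| Equal, s = 0.90 | 0.659 | 0.660 | 0.660 | 0.660 |
| Maze arm only, s = 0.90 | 0.653 | 0.753 | 0.754 | 0.655 |
| Opposite, s = 0.90 | 0.646 | 0.852 | 0.852 | 0.649 |
| Opposite, s = 0.80 | 0.646 | 0.809 | 0.810 | 0.653 |

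The planned imputation and complete cases agree within 0.001 on average. Within single trials they differ by about 0.015 (simulation noise), with correlation about 0.997.

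Standard errors of the log odds ratio, SAP imputation against imputation with earlier rhythm: 0.231 and 0.223 in the first row (3.5% smaller), 0.236 and 0.231 in the last (2.1% smaller). Complete-case standard errors match those of the planned imputation to within 0.001. In the maze-only scenario the bias is (0.753 − 0.653)/0.233 = 0.43 standard errors.

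**The case against.** A reader might infer that the plan leaves a definite bias which existing ECGs would remove. The document does not support that, for four reasons.

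- **Earlier rhythm is not certain.** SAP 4.3 ties no ECG to 6 weeks or 6 months. The plural wording, and the description in 4.2 of the baseline recording as the first, make a 6-month ECG a fair reading and no more. The certain 24-month record will usually be absent for patients lost before 12 months; it helps those who missed only the 12-month recording.
- **Dependence on rhythm alone is not enough.** On the planned odds-ratio scale it must differ between arms. Patients are meant to be blind to allocation (SAP 1.2), which makes this less plausible, though not impossible.
- **The sizes are illustrative.** No figure in the SAP supports the loss gradients. The 12% also covers deaths, whereas 2.3 names only withdrawal and loss, so the share open to improvement, and the bias with it, may be smaller.
- **The near-complete removal of bias is by construction.** Every lost patient in the simulation had an earlier rhythm on record, and loss depended on that rhythm.

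The plan will also examine missingness by arm and, above 5% loss, tests a departure by setting lost patients to AF.

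All of this stands and limits the claim. It does not rescue the imputation, which is redundant in every scenario. Nor does it touch the 24-month point, which needs no assumption about a 6-month ECG.

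**Conclusion.** The imputation in SAP 2.3 adds nothing to complete cases for the 12-month endpoint. This follows from the two variable lists and does not depend on the loss pattern. It assumes that surgeon enters both models in a similar way; the SAP does not say how surgeon enters the imputation.

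Whether bias results is conditional. It needs loss that depends on post-operative rhythm differently by arm, and its size and direction rest on assumed rates. With equal dependence the odds ratio is essentially unbiased, and the gain from better imputation is the 2-4% reduction in standard error.

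Any bias can be reduced only where rhythm or a related measure was recorded before loss, or at 24 months for a patient who missed only the 12-month recording. Drug use and EQ-5D at the early visits are certain to be scheduled, but the document does not show how well they predict rhythm. The change is worth making because it costs almost nothing and concerns a primary endpoint, not because a bias has been shown.

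**What to change.** - **SAP 2.3 and 5.4.1:** keep baseline heart rhythm, surgeon, surgical procedure (as worded) and treatment group in the imputation model. Add, by treatment arm, post-operative rhythm at every visit where it is recorded, including 24 months, together with early post-operative drug use and EQ-5D. Name the same predictors in both sections.
- **SAP 5.6:** use the same joint imputation, so that 12-month rhythm informs missing 24-month rhythm. Keep the available-case 24-month analysis alongside.
- **Visits with rhythm data:** state which visits include an ECG, so that the predictor list is fixed in advance.

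The cost is SAP wording and a slightly larger imputation model. No new data, visits or patients are needed, and the primary analysis model stays as it is.
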